11.4.1. Inclusion and Exclusion Criteria

The following values from subject's medical record are required to demonstrate that the subjects meet the BSC's labeled indication for CRT-D implantation:

BSC approved labeling verification in US

- LVEF and date of measurement (*It is required that the LVEF value be measured no more than 6 months prior to the CRT-D implantation*).
- QRS duration
- Bundle Branch Block morphology (LBBB or non-LBBB)
- Heart failure etiology (ischemic or non-ischemic)
- NYHA class
- Cardiovascular medications

BSC approved labeling in Europe

Subjects who are at risk for sudden cardiac death caused by ventricular arrhythmias and who have heart failure (including asymptomatic [NYHA Class I] ischemic heart failure) with ventricular dyssynchrony.

11.4.2. Subjects Demographics

Subject's age and sex. Race/ethnicity are only required in US.

11.4.3. Medical History

Subject's history of cardiovascular diseases is required to be collected.

11.4.4. Subject Physical Assessment

Physical presentation will be used to provide an assessment of the subject's condition and changes in clinical symptoms. Evaluation includes:

- Resting heart rate
- 12-lead ECG (if available)
- Blood pressure
- Height/weight
- Presenting symptoms
- Echo post-implant data (if available)

11.4.5. NYHA Class Assessment

The subject's current New York Heart Association (NYHA) Class must be determined based on Table 11.4-1.

Table 11.4-1: NYHA Classifications

Class	Patient Symptoms
I	No limitation of physical activity. Ordinary physical activity does not cause undue fatigue, palpitation, dyspnea (shortness of breath).
II	Slight limitation of physical activity. Comfortable at rest. Ordinary physical activity results in fatigue, palpitation, dyspnea (shortness of breath).
III	Marked limitation of physical activity. Comfortable at rest. Less than ordinary activity causes fatigue, palpitation, or dyspnea.
IV	Unable to carry on any physical activity without discomfort. Symptoms of heart failure at rest. If any physical activity is undertaken, discomfort increases.

11.4.6. Cardiac Medications

Subject current cardiovascular medications uses are required. For study purposes, cardiac medications include: diuretics, ACE inhibitors/angiotensin receptor blockers, beta blockers, aldosterone antagonists, Nephilysin inhibitors, Class I/III antiarrhythmics, calcium channel blockers, anti-hypertensive drugs, and statins.

11.4.7. Implanted System Information

The following data are required to be collected from the implanted CRT-D device, RA lead, RV lead, and quadripolar LV lead:

- Manufacturer
- Model number
- Serial number (optional for non-BSC leads)
- Implant date
- Report if it was a *de novo* implant or a device upgrade (from pacemaker or ICD)
- Battery consumption data: Time to explant need to be collected

11.4.7.1. LV Lead Location

The coronary venous LV lead location data are required if such information is available from reviewing lead imaging documents including in-procedure fluoroscopy or pre-discharge

chest X-rays, or can be obtained from the implanter's dictation in the subject's medical record.

The LV lead location will be classified and recorded in eCRF as follows:

- Anterior, anterolateral, lateral, posterolateral, or posterior

And

- Basal, Middle, and Apical

11.4.8. Current Device Setting and Status

After initial device interrogation, print a copy of the Combined Report and Settings Report to document current device settings and status prior to conducting any test and changing the programming settings.

11.4.9. Battery Consumption

The following values are required to be collected:

- Time to explant

11.4.10. Lead Measurements

The following lead measurements are required for RA lead, RV lead, and LV lead:

- Intrinsic amplitude (mV)
- Pacing capture threshold (PCT in V/ms; the recommended pulse width is 0.4ms)
- Pacing lead impedance (Ω)
- Shocking lead impedance (Ω , RV lead)
- Phrenic Nerve Stimulation (PNS) Threshold (V LV lead)

The following document is required for RA lead, RV lead, and LV lead measurements:

- Device follow-up report

Lead measurement testing is required unless a rationale is provided. For example, the measurement is prohibited by a subject's condition.

- The pacing configurations used in the LV lead measurement testing are per the investigator's discretion. It is recommended that at least one configuration must be tested for the LV lead, and it is recommended that it be the configuration that is planned for the final programming.

The threshold should be defined as one voltage level above the level where two non-captured beats are observed. If multiple PCT tests were performed, only the final measurement is required to be entered on the eCRF.

11.4.11. Optimization features information

Each site should be using Optimization features or any other method as per their site SOC.

11.4.11.1. SmartDelay Feature Data

If the SmartDelay test is done per site SOC to obtain programming recommendations for the AV Delay and Pacing Chamber. It is per the investigator's discretion whether to follow the programming recommendations.

If SmartDelay test is done, the following values are recommended to be obtained:

- Sensed AV delay (SAV) and Paced AV delay (PAV), both recommended and final programmed value (Print a copy of Settings Changes Report. This report will display recommended SAV, PAV and Pacing Chamber). Keep this printed report at the Subject File.
- Pacing Chamber (BiV or LV Only), both recommended and final programmed values.
- Rationale if the SmartDelay recommendations are not followed.
- A sense to RV sense interval, A sense to LV sense interval, A pace to RV sense interval and A pace to LV sense interval

If the SmartDelay test is done, the following document is required:

- Print a copy of the Settings Changes Report immediately after running the SmartDelay test and before any other changes in settings are made and programmed. This report will display the recommended changes to the SAV, PAV, and Pacing Chamber at pending status.

For a step-by-step guidance on performing the SmartDelay test, see Appendix 0.

11.4.11.2. LV VectorGuide feature Data

If LV VectorGuide test is done per site SOC and completed, provide the number of viable pacing vectors.

Subjects must have LV and RV sensed beats for test to be successful. If the subject does not tolerate low rate RV pacing, stop the test and provide the rationale of not completing the test.

The following values are recommended to be obtained when VectorGuide is performed:

- Number of viable pacing vectors.
- RV-LV delay (Is RV-LV test run? If Yes, capture the values)
- Impedance (Is Impedance test run? If Yes, out of bounds? Yes or No)
- PNS (Is PNS test run? If Yes, at which tested threshold and Is PNS present)
- Pacing Capture Threshold (Is Quick Capture test run?)

- if Yes, capture the tested threshold and whether it is captured or not;
- If No, Is Auto or Manual threshold test run? If yes, capture the pacing capture threshold)

If the LV VectorGuide test is done, the following document is required:

- Print a copy of the VectorGuide Report

For a step-by-step guidance on performing the LV VectorGuide test, see Appendix 26.2.

11.4.11.3. LV MSP feature Data

For subjects with LV MSP feature enabled, it is required to use VectorGuide to assess viable LV pacing vectors from all tested pacing vectors. It is recommended to use the pacing vectors recommended by SmartVector test; however, final selection of the pacing vectors is per investigator's discretion.

The following values are required for subjects with LV MSP enabled:

- RV-LV delay value for all 4 electrodes as cathode: E1-Tip1, E2-Ring2, E3-Ring3, E4-Ring4
- LV pacing impedance for all tested vectors
- Phrenic Nerve Stimulation (PNS) test results for all tested vectors
- LV Quick Capture threshold test
- Number of viable pacing vectors

For subjects with LV MSP feature enabled, the LV pacing vectors will be recommended by the required SmartVector test; however, since it is not required to follow the recommendation from SmartVector, final pacing configurations for PCT measurement are per the investigator's discretion.

Investigator rationale is required commended if investigator not following LV MSP final pacing configuration feature recommendations.

MSP SmartVector Test (only for subjects with MSP turned on)

- LVa and LVb, both the recommended and final programmed values.
- Rationale if the LVa and LVb recommendations are not followed.

For a step-by-step guidance on performing SmartVector operation, see Appendix 26.3

MSP SmartOffset Test (only for subjects with MSP turned on)

- SmartOffset values, both the recommended and final programmed values.
- Rationale if the SmartOffset recommendations are not followed.

For a step-by-step guidance on performing SmartOffset operation, see Appendix 26.4

11.4.11.4. HeartLogic feature Data

HeartLogic alerts only can be available via the LATITUDE Remote Monitoring System.

For subjects with HeartLogic feature enabled, data may be collected via LATITUDE. HeartLogic feature usage throughout the follow-up period will be collected along with changes to alert thresholds and review of sensor trends with the data collected via LATITUDE system. The following data are to be collected in the eCRFs:

- HeartLogic alert programming: On or Off
- Any change in subjects' treatment plan based on the HeartLogic alerts (if available)

11.4.11.5. Other optimization methods information

Data about any other method used to optimize subject A-V delay need to be collected in this section: Echo optimization, Fixed A-V delay programming, etc.

11.4.12. Final Device Settings and Status

Print a copy of the Combined Report and Settings Report for all subjects at the end of the visit and clear the device counters as the final step.

11.4.13. Adverse Events Assessment

Study required adverse event will be collected and assessed for each eligible subject after signing of the informed consent. See Section 19.1 for Adverse Event collection and reporting requirement.

A summary of the source documentation required at Enrollment Clinic Visit is described in **Table 11.4-2**.

Table 11.4-2: Source Documentation Required at Enrollment Visit

Data Collection Requirement	Retention of Original Source Documentation

 • Informed consent form and process, including informed consent signature and date • Inclusion and exclusion criteria • Cardiovascular Medical History • NYHA Class assessment • Physical Assessment • Cardiac Medication • Reportable Adverse Events, Device Deficiencies (if applicable) 	Study Center

 • Echocardiogram post implant data (if available) 	Study Center

 • 12-lead ECG (if available) 	Study Center

 • Device and leads information • Device Settings Report (at the beginning and at the end of the visit) 	Printed reports will remain at Study Center

• Device features used report (if applicable)• Device Combined Report (at the beginning and at the end of the visit)	
---	--

11.5. 12 months Clinic Visit

The 12 months Clinic Visit is must be performed at 330-390 calendar days post Enrollment Visit (*Required*)

Subjects with LATITUDE remote monitoring system may have their device performance and diagnostic data downloaded remotely from the LATITUDE BSC team during these visits timeframe. The device data transmission via LATITUDE will not be replacing the Clinic Visit.

An overview of data to be collected at 12 months Clinic Visit is provided below, with further details followed in the sections below:

- Subject Physical Assessment
- Cardiac Medication Changes
- NYHA class assessment
- Patient Global Assessment (PGA)
- Physician Global Assessment (PhGA)
- HF hospitalization information
- Device Initial Interrogation to capture current settings, programming and status (including battery consumption) at the beginning of the Clinic Visit
- Changes in programming or features since the last Clinic Visit
- Lead measurements
- BSC Optimization features data: SmartDelay test and value (if done), LV Vector Guide test and value (if done), LV MSP (if enabled), SmartVector and SmartOffset value (if done), HeartLogic information (if applicable) and other optimization methods as per site SOC
- Final device programming, settings and status (including battery consumption) at the end of the Clinic Visit before subject will leave the site.
- Adverse Events Assessment

11.5.1. Subject Physical assessment

Physical presentation will be used to provide an assessment of the subject's condition and changes in clinical symptoms following instructions from Section 11.4.4.

11.5.2. Cardiac Medication Changes

Subject current cardiovascular medications changes only from their last study visit (increase, decrease, new or removed). Medications collected include: diuretics, ACE inhibitors/angiotensin receptor blockers, beta blockers, aldosterone antagonists, Nephilysin inhibitors, Class I/III antiarrhythmics, calcium channel blockers, anti-hypertensive drugs, and statins.

11.5.3. NYHA Class Assessment

The subject's current NYHA Class must be determined based on Table 11.4-1.

11.5.4. Physician Global Assessment

The current Physician Global Assessment (PhGA) will be filled out by the investigator/delegated site staff based on the evaluation of the subject's status from multiple clinical aspects. A comparison of the assessment tool for the PGA and PhGA is shown in **Table 11.5-1: Global Assessment Tool: Physician Global Assessment (PhGA) and Patient Global Assessment (PGA)**Table 11.5-1Error! Reference source not found..

11.5.5. Patient Global Assessment

The current PGA must be filled out by the subject, as specified in the Assessment Tool in Table 11.5-1Error! Reference source not found..

Table 11.5-1: Global Assessment Tool: Physician Global Assessment (PhGA) and Patient Global Assessment (PGA)

Physician Global Assessment (PhGA)	Patient Global Assessment (PGA)

How is the patient's clinical status today compared to his or her status at the time of baseline?
 
• Markedly improved• Moderately improved• Mildly improved• No change• Mildly worse• Moderately worse• Markedly worse	
How do you feel today compared to how you felt when you started the study?
 
• Very much better• Much better• A little better• No change• A little worse• Much worse• Very much worse

11.5.6. Definition and Components of the Clinical Composite Score

The Clinical Composite Score (CCS) will be calculated for all subjects at the 12 Month Visit. The CCS consists of the following components:

- All-cause mortality
- Heart Failure (HF) hospitalization
- Patient Global Assessment (PGA)
- NYHA class

11.5.6.1. HF Hospitalization Definition

For the purpose of the CCS calculation, HF hospitalization is defined as an HF event with a primary cause of HF and either of the conditions below is met:

- Subject is admitted and discharged with a calendar date change.
- Subject is not hospitalized but received one or more IV medications including diuretics, inotropes, vasodilators, other parenteral therapy, or aquapheresis

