5.2. Other Devices

Any commercially available Right Atrial (RA) lead, Right Ventricular (RV) lead and quadripolar LV lead from any manufacturer is eligible in the study.

6. Study Objectives

The primary objective in this study is to learn in a general CRT-D population, which optimization techniques are used and how effective they are. It will compare 12-month response rates among different optimization methods and characterize which selected patient subgroups achieve better response than others.

A subset of SMART Registry subjects will contribute to the NG4 Post Market Clinical Follow-Up (PMCF) Cohort whose objective is collecting data on the NG4 CRT-D features and device usage in a real world setting and monitor long term safety associated with these devices to support CE Mark.

7. Study Endpoints

The primary endpoint will evaluate the CRT Response rate among Full Registry subjects at 12 months, defined by a Clinical Composite Score (CCS) consisting of:

- All-cause mortality
- Heart failure events
- NYHA Class
- Quality of life (patient Global Assessment instrument)

For the NG4 PMCF Cohort the primary endpoint will be NG4 PG related complication free rate at 36 months.

SMART Registry Entire Cohort

The Clinical Composite Score developed by Packer will be evaluated to determine CRT Response in the entire SMART Registry cohort and in selected subgroups^{4, 17}. The CCS will be evaluated at 12 months and consists of all-cause mortality, heart failure events, NYHA class and quality of life as assessed by the patient Global Assessment instruction. CRT response status for each subject will be determined by the CCS, with CRT response classified as improved, unchanged or worsened.

NG4 PMCF Cohort

In the subjects included in the NG4 PMCF Cohort, the NG4 PG-related complication free rate (CFR) at 36 months will be evaluated. The PMCF Primary Endpoint will evaluate the safety of the NG4 device when LV MSP is enabled.

8. Study Design

This is a global, multicenter, prospective, observational, single-arm post market study (Registry), including the NG4 PMCF necessary to support NG4 CE Mark.

8.1. *Scale and Duration*

The study will be conducted at up to 200 sites globally. Approximately 2000 subjects will be enrolled in Europe, United States, Canada and Asia Pacific, and sites may continue to enroll subjects until notified of enrollment completion.

SMART Registry Entire Cohort

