19.1. Reportable Events by investigational site to Boston Scientific

It is the responsibility of the investigator to assess and report to BSC any event which occurs in any of following categories:

- All Serious Adverse Events
- All Adverse Device Effects
 - Events listed in the arrhythmia logbook, should be reported only if determined to be clinically significant by the investigator and/or delegated site staff (i.e. ATR, PMT, etc.)
 - Any new onset/diagnosis of VT/VF requiring anti-arrhythmic therapy, or per the PI, clinically worsening VT/VF requiring Therapy. (Appropriate VT therapy that is not considered clinically worsening per the PI is not to be reported).
- All Device Deficiencies
- Unanticipated Adverse Device Effects/Unanticipated Serious Adverse Device Effects
- All Heart Failure (HF) and All Cardiac related adverse events requiring IV or invasive therapy, including new onset cardiac events, or worsening in severity or frequency of pre-existing conditions.

An adverse event is deemed as a HF Event if the primary cause is HF and either of following conditions is met:

- In-patient hospitalization \geq 24 hours
- No hospitalization but received one or more IV medications including diuretics, inotropes, vasodilators, other parenteral therapy, or aquapheresis.

Adverse event collection begins after the subject signs the informed consent. Events which occur prior to the signing of the informed consent form, and per the investigator/delegated site staff are a result of the device implant procedure should not be reported. Even if such event requires a treatment that is executed after the informed consent is signed. (e.g. hematoma that requires intervention is not an adverse event as long as it does not worsen after consenting; infection at the incision site is not an adverse event as long as it does not worsen after consenting; planned medical procedure or lead revisions are not adverse events as long as the event is identified prior to the consent). These are considered preexisting conditions and are not reportable. If the event worsens after consenting and meets criteria for a reportable event then they must be reported (e.g. hematoma that is worsened and requires intervention; a new infection at the incision site or an infection that is worsened and requires

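### The CCS heart failure component is not reconciled with the plan's only definition of an HF event, and read literally both rules leave out a same-day admission treated with IV therapy

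*Combined protocol and SAP*

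**What the plan says.** The component has two names. The synopsis, Section 7 and Section 12.3.1 list it as "Heart failure events", and Section 7 says that the CCS "consists of all-cause mortality, heart failure events, NYHA class and quality of life". Sections 4, 11.5.6, 11.5.6.3 and 27.2 call it HF hospitalization.

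Section 11.5.6.1 gives the scoring rule: "For the purpose of the CCS calculation, HF hospitalization is defined as an HF event with a primary cause of HF and either of the" two conditions that follow. The first is "Subject is admitted and discharged with a calendar date change". The second is "Subject is not hospitalized but received one or more IV medications including diuretics, inotropes, vasodilators, other parenteral therapy, or aquapheresis".

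Section 19.1, on events that sites report to the sponsor, holds the only definition of an HF event: "An adverse event is deemed as a HF Event if the primary cause is HF and either of following conditions is met". Its first condition is an in-patient stay of at least 24 hours. Its second is "No hospitalization but received one or more IV medications including diuretics, inotropes, vasodilators, other parenteral therapy, or aquapheresis".

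Under Section 11.5.6.3, one HF hospitalization makes a subject Worsened and rules out Improved, whatever the NYHA class or PGA shows.

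**The concern.** There are two separate problems.

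The first is which rule applies. Section 11.5.6.1 is built on the term *HF event*, and the only definition of that term has a different admission condition. The endpoint sections also use the event wording. A programmer deriving the CCS could apply 11.5.6.1 alone, or could first screen events through 19.1.

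The second problem exists whichever rule applies. In both sections the IV-therapy condition is limited to subjects who were not hospitalized. An admission that begins and ends on one calendar day fails the admission condition for length and the IV condition for status. The plan treats outpatient IV therapy for heart failure as enough for Worsened, so it is inconsistent for the same treatment to score nothing because the patient was formally admitted.

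What is at stake is the level assigned to individual subjects on the primary endpoint. Where NYHA class or PGA has improved, the wording alone can decide between Improved and Worsened.

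**Working it through.** **Inputs.** The two conditions in Section 11.5.6.1, the two in Section 19.1, and the level rules in 11.5.6.3. The plan gives no HF event rate and no frequency of short stays, so it has no figure of its own to reproduce for this component.

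**The rules in logical form.** For an episode with HF as primary cause, let A = admitted, D = calendar date change, H = stay of at least 24 hours, V = IV therapy or aquapheresis.

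- 11.5.6.1 alone: (A and D) or (not A and V)
- 19.1 alone: (A and H) or (not A and V)
- 11.5.6.1 with 19.1 read into it: both must hold. A stay of at least 24 hours always crosses midnight, so H implies D and this reduces to the 19.1 rule.
- 11.5.6.1 with the admission-status condition removed from its second limb: (A and D) or V

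| Episode | 11.5.6.1 alone | 19.1, or both together | Second limb reworded |
|---|---|---|---|
| Stay of 24 h or more | counts | counts | counts |
| Overnight, under 24 h, IV therapy | counts | does not count | counts |
| Overnight, under 24 h, no IV therapy | counts | does not count | counts |
| Same-day admission, IV therapy | does not count | does not count | counts |
| Same-day admission, no IV therapy | does not count | does not count | does not count |
| Outpatient, IV therapy | counts | counts | counts |
| Outpatient, no IV therapy | does not count | does not count | does not count |

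The sections disagree only on overnight stays under 24 hours. They agree in omitting the IV-treated same-day admission, and this is the only row that the rewording changes relative to 11.5.6.1.

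**Effect on the level.** A subject whose only qualifying episode is an IV-treated same-day admission, and who has no worsening on NYHA class or PGA, is scored Improved if either has improved and Unchanged otherwise. A subject who died, or worsened on NYHA class or PGA, is Worsened in any case.

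**Scale, by assumption only.** Let q be the share of 2000 subjects for whom an IV-treated same-day admission is the only worsening criterion. The number changing level is at most 2000 × q:

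- q = 0.2%: 4 subjects (0.2 points)
- q = 0.5%: 10 subjects (0.5 points)
- q = 1%: 20 subjects (1.0 point)
- q = 2%: 40 subjects (2.0 points)

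For comparison, the 95% CI width at n = 2000 is 2 × 1.96 × √(p(1−p)/2000). This is 4.4 points at p = 0.5 and 4.1 points at p = 2/3, both within the plan's 5% limit. A move from Unchanged to Worsened leaves the Improved proportion as it was and affects only the Improved/Unchanged versus Worsened grouping in Section 12.3.1. A move from Improved to Worsened affects both groupings.

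**The case against.** The best defence is that Section 11.5.6.1 is self-contained. It is expressly written for the CCS, states its own cause criterion and both conditions, and does not cross-refer to Section 19.1, which is a reporting rule that never mentions the CCS. If 19.1 were imported, the date-change condition would decide nothing, as the working shows. This is the more natural reading, and it stands: a reader might infer that both definitions feed the primary composite, but the text does not establish that. What remains is that 11.5.6.1 uses a term defined only in 19.1, that the endpoint sections use that label, and that no order of precedence is given.

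On same-day admissions, *hospitalized* is not defined in 11.5.6.1. Its two conditions could be read as complementary, so that a stay without a date change counts as not hospitalized. A site might record it that way. This makes the exclusion a consequence of the literal wording rather than a certainty, but it does not supply a rule.

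It is also fair that the events are not lost. Section 19.1 makes HF events needing IV therapy reportable whatever the length of stay, Table 19.2-1 makes in-patient hospitalization a serious adverse event, and under Section 21.1 the sponsor's Medical Safety group classifies events. The gap lies in classification rather than in reporting, so it can be closed before analysis.

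Finally, this is an exploratory registry with no formal hypothesis on this endpoint. That limits the consequence but does not remove the need for one scoring rule.

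**Conclusion.** The point holds as an unresolved definition with a literal gap in a component of the primary endpoint. Overnight stays under 24 hours count under the CCS-specific text and drop out if 19.1 is read into it; the former is the better reading, but the plan does not say so. An IV-treated same-day admission scores nothing under either section as worded, although the same treatment in an outpatient makes the subject Worsened.

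The number affected cannot be derived from the documents. The 4–40 subjects are an upper bound under an assumed 0.2–2%, cover same-day admissions only, and suppose that all 2000 subjects are analysed. No size can be given for the overnight stays.

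Three stronger conclusions are tempting but unsupported. A reader might infer that the Worsened level is in fact misclassified; the documents show only that it can be, since other criteria or site recording may already give the right level. A reader might size the problem from all IV-treated stays under 24 hours, but that mixes overnight stays, which 11.5.6.1 already counts, with the same-day stays it omits. A reader might also expect the error to fall unevenly across optimization methods because these follow site practice, but no section says that sites or countries label short stays differently.

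**What to change.** 1. State that the definition in 11.5.6.1 governs the CCS.
2. Use one term for the component in the synopsis and in Sections 7, 11.5.6 and 12.3.1.
3. Align the HF event definition in 19.1, or state there that it does not apply to the CCS.
4. Reword the second condition of 11.5.6.1 so that IV HF therapy or aquapheresis for a primary HF cause counts whether or not the subject was admitted.
5. Confirm that the eCRF captures admission and discharge dates. Section 11.5 mentions only HF hospitalization information, and Table 19.4-1 mentions the event date and treatment, so the documents do not show that these fields exist.

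Section 12.3.5 allows changes to the planned analyses to be recorded in a Statistical Analysis Plan approved before analysis, and the scoring rule should be fixed by then. The cost is wording in a few sections, eCRF guidance, and a date field if one is missing. The downside is that the Worsened share may rise slightly.
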